I agree to comply with the current International Council for Harmonisation of Technical Requirements for Pharmaceuticals for Human Use (ICH) Guideline on Good Clinical Practice and applicable regulations and guidelines.

I agree to ensure that financial disclosure statements will be completed by:

- me (including, if applicable, my spouse (or legal partner) and dependent children);
- my Sub-investigators

before the start of the study and to report any changes that affect my financial disclosure status for up to 1 year after the study is completed.

I agree to ensure that the confidential information contained in this document will not be used for any purpose other than the evaluation or conduct of the clinical investigation without the prior written consent of Vifor Pharma.

Signature by the Investigator on this Protocol Signature Page documents review, agreement and approval of the requirements contained within this protocol.

Signature

Date (DD.MMM.YYYY)

Name of Principal Investigator

SYNOPSIS

VIT-IRON-2011-004

Title:	An open-label, randomised controlled multi-centre study to assess the impact of ferric carboxymaltose in correcting iron deficiency anaemia compared with Venofer® (Iron Sucrose) in Chinese subjects
Short Title:	China Phase 3 Study
Study Product(s):	Ferinject® (ferric carboxymaltose, FCM)
Indication:	Iron deficiency anaemia (IDA)
Phase:	3
Sponsor:	Vifor Pharma
Study Code:	VIT-IRON-2011-004
Co-ordinating Investigator:	

Objectives:	
Primary Objective(s):
 
 To demonstrate the efficacy of ferric carboxymaltose (FCM) given in a simple dosing regimen in correcting IDA, by demonstrating non-inferiority to treatment with the currently approved intravenous (IV) iron therapy of Iron Sucrose (IS, Venofer) in the Chinese population. 
Secondary Objective(s):
 
 To assess the safety of FCM compared to IS in the Chinese population. To evaluate the effect of FCM compared to IS on relevant laboratory parameters (haematology, chemistry, iron parameters) in the Chinese population.
Design:	
Open-label, randomised controlled study to assess the impact of FCM in correcting IDA compared with Venofer (IS).
 
All subjects, after providing written informed consent and meeting the eligibility criteria, will receive a first dose of IV iron as either FCM or IS. A total of approximately 368 subjects (184 per group) will be randomised. All subjects will have IDA as measured by haemoglobin (Hb), serum ferritin and transferrin saturation (TSAT) at screening.
 
Ferric carboxymaltose will be administered as either a diluted infusion or undiluted injection (at Investigator's discretion) at single, maximum daily doses of 500 or 1,000 mg iron) and IS will be administered as an undiluted bolus push injection or diluted infusion (with each single injection/infusion of 200 mg iron). Note, for subjects randomised to receive IS, dosing visits are required three times a week to achieve total iron repletion dosing as calculated using the Ganzoni formula.
 
For subjects randomised to FCM, the total iron requirement will be calculated at baseline based on the screening Hb and body weight (BW). Dosing will be at baseline (Day 1) and, if required, at Day 8 and Day 15..

Design (Cont'd):	All subjects will attend study visits at screening, baseline and thereafter at Weeks 2, 4 and 6. All subjects will attend an end of study visit (at Week 8 – or earlier if discontinued prematurely). Additional dosing visits may be required for subjects receiving IS three times weekly up to Week 4.																														
Treatment:	

Arm A: Ferric Carboxymaltose

Dosing to be based on subject Hb and BW at screening as per table below:

Total Iron (mg) as FCM	

	BW 35-<70 kg¹	BW ≥70 kg		

	Hb <10 g/dL	Hb ≥10-<14 g/dL	Hb <10 g/dL	Hb ≥10-<14 g/dL		

Day 1	1,000 mg	1,000 mg	1,000 mg	1,000 mg		

Day8	500 mg	No dose	1,000 mg	500 mg		

1.

Notes:

BW = Body weight; FCM = Ferric carboxymaltose; Hb = Haemoglobin. The maximum single dose that should be given to a subject is 20 mg/kg BW, therefore for subjects with BW 35 - <50kg and Hb ≥ 10 g/dL, the 1,000 mg dose should be split into 2 x 500 mg (one 500 mg dose on Day 1 and one 500 mg dose on Day 8. Subjects with BW 35 - <50 kg and Hb < 10g/dL should receive 3 doses of 500 mg (on Day 1, 8 and 15) .

To be administered as undiluted injection or diluted infusion (500 mg iron diluted in 100 mL 0.9% w/v physiological saline or 1,000 mg iron diluted in 250 mL 0.9% w/v physiological saline) over at least 5 minutes for the 500 mg dose and over at least 15 minutes for the 1,000 mg dose. Administration time should not exceed 30 minutes for either the 500 or the 1,000 mg dose.

Arm B: Venofer (Iron Sucrose)

Required total iron dose to be calculated per label (Ganzoni formula):

Cumulative iron deficit [mg] (calculated from screening values)= BW [kg] x (target Hb⁽¹⁾ - actual Hb) [g/dL]⁽²⁾ x 2.4⁽³⁾ + 500 mg⁽⁴⁾

(1)

Target Hb for BW >35 kg = 15 g/dL, respectively 9.3 mmol/L

(2)

To convert mmol/L to g/dL: multiply Hb (mmol/L) by the factor 1.61145

(3)

Factor 2.4 = 0.0034 (iron content Hb = 0.34%) x 0.07 (blood volume = 7% of BW) x 10,000 (conversion g/dL to mg/L x 10)

(4)

Storage iron

Note: BW = Body weight.

The calculated iron dose will be split into doses of 200 mg iron administered by slow intravenous injection at a rate of 1 ml undiluted solution per minute (10 ml of the product in at least 10 minutes; administration time should not exceed 60 minutes) or by drip infusion in a dilution of 1 ml of Venofer in a maximum of 20 ml 0.9% w/v physiological saline (10 ml of the product in maximum 200 ml of saline). The drip infusion rate should be 200 ml solution in at least 30 minutes and should not exceed 60 minutes. The subjects will be administered Venofer three times a week, with an initial dose at baseline and will receive iron, as per approved label, until the subject has received the calculated iron dose. The calculated cumulative Venofer dose will rounded up or down to the nearest 200 mg.

	Total Iron (mg) as FCM							BW 35-<70 kg ¹		BW ≥70 kg				Hb <10 g/dL	Hb ≥10-<14 g/dL	Hb <10 g/dL	Hb ≥10-<14 g/dL		Day 1	1,000 mg	1,000 mg	1,000 mg	1,000 mg		Day8	500 mg	No dose	1,000 mg	500 mg	
Total Iron (mg) as FCM																															
	BW 35-<70 kg ¹		BW ≥70 kg																												
	Hb <10 g/dL	Hb ≥10-<14 g/dL	Hb <10 g/dL	Hb ≥10-<14 g/dL																											
Day 1	1,000 mg	1,000 mg	1,000 mg	1,000 mg																											
Day8	500 mg	No dose	1,000 mg	500 mg																											
Inclusion Criteria:	

1.

At least 18 years of age

 

2.

Hb <11 g/dL (females) or Hb <12 g/dL (males) at the screening visit

 

3.

Serum ferritin <100 ng/mL for subjects with underlying inflammatory disease (e.g., inflammatory bowel disease (IBD), chronic kidney disease

																														

[figure not shown]
	
(CKD) or chronic heart failure (CHF), as determined by high sensitive C-reactive protein [hsCRP] levels above the normal range) otherwise serum ferritin ≤ 14 ng/mL in subjects with no apparent underlying inflammatory disease (as determined by hsCRP levels within normal range) at the screening visit
 
 4. TSAT $< 16\%$ (any subject) at the screening visit 5. Microcytic, hypochromic anaemia at the screening visit, defined as: 
 a. Mean corpuscular Hb concentration (MCHC) $< 32\%$ b. Mean corpuscular volume (MCV) < 80 fL c. Mean corpuscular Hb (MCH) < 27 pg 6. Subjects with the ability to understand the requirements of the study and abide by the study restrictions, and who agree to return for the required assessments 7. Before any study-specific procedure is conducted, the appropriate written informed consent must be obtained
--	--

Exclusion Criteria:	
 1. Subject has known hypersensitivity to any of the products to be administered during dosing 2. Any history of iron storage diseases such as haemochromatosis 3. Any history or clinical findings of iron utilisation disorders such as sideroachrestic anaemia 4. Known haemoglobinopathy (e.g. thalassaemia) 5. Any history or clinical findings of anaemia associated with: 
 a. Haematuria b. Vitamin B12 or folic acid deficiency that requires treatment (subjects can be included after deficiency is corrected) 6. Any allergic predispositions, i.e. any history of asthma or atopic allergy. This includes drug allergies. 7. Planned surgery with anticipated blood loss (defined as Hb drop >2 g/dL) in the 3 months post randomisation 8. Subject has known malignancy (with or without current treatment), except basal cell or squamous cell carcinoma of the skin or cervical intra-epithelial neoplasia 9. Haemodialysis (current or planned within the next 3 months) 10. History of IV iron therapy, erythropoiesis stimulating agent (ESA) therapy and/or blood transfusion in previous 4 weeks prior to baseline, and oral iron or oral iron-containing products including Chinese herbal medicines (>75mg iron/day) in the 7 days prior to baseline 11. Body weight <35 kg 12. Chronic liver disease and/or screening alanine transaminase (ALT) or aspartate transaminase (AST) above 3 times the upper limit of the normal range 13. Known human immunodeficiency virus infection, acquired immunodeficiency syndrome, tuberculosis 14. Known active hepatitis B or C or other active infection (acute or chronic) 15. Subject currently is enrolled in or has not yet completed at least 30 days since ending other investigational device or drug study(ies), or subject is receiving other investigational agent(s) 16. Subject is pregnant or is breast feeding 17. Female subject of childbearing potential not using adequate contraceptive methods during the study and for up to 1 month after the last dose of the study medication. Adequate contraceptive methods are defined as those which result in a low failure rate (i.e., less than 1% per year) when used consistently and correctly such as implants, injectables, combined oral contraceptives, some intra-uterine devices, sexual abstinence or vasectomised partner. Non-childbearing potential includes being surgically sterilised at least 6 months prior to the study or post-menopausal, defined as amenorrhoea for at least 12 months 18. Male subjects planning to father a child within 7 days from the last study drug administration. 19. Subject has any kind of disorder that compromises the ability of the subject
---------------------	---

	to give written informed consent and/or to comply with study procedures and/or other reason(s) that render subject not appropriate for study participation in the opinion of the treating physician
Primary and Secondary Endpoints:	
Primary Endpoint:
 
 Percentage of subjects achieving an increase in Hb of ≥ 2 g/dL (responders) from baseline at any time up to Week 8 
Secondary Endpoints:
 
Efficacy:
 
 Percentage of subjects achieving an increase in Hb ≥ 2 g/dL from baseline at Weeks 2, 4, 6 and 8 Change in Hb from baseline to Weeks 2, 4, 6 and 8 The percentage of subjects with TSAT $\geq 16\%$ and serum ferritin ≥ 100 ng/mL (for subjects with underlying inflammatory disease as determined by hsCRP levels above the normal range) or serum ferritin > 14 ng/mL (in subjects with no apparent underlying inflammatory disease as determined by hsCRP levels within normal range at screening) at Weeks 2, 4, 6 and 8 Change in TSAT from baseline to Weeks 2, 4, 6 and 8 Change in serum ferritin from baseline to Weeks 2, 4, 6 and 8
	
Secondary Endpoints (Cont'd):
 
Safety:
 
 Change in laboratory parameters (haematology, clinical chemistry and iron status) from baseline over the study duration Summary of all treatment emergent adverse events (TEAE): type, nature, incidence and outcome overall and by underlying disease aetiology Summary of changes in vital signs from baseline to Weeks 2, 4, 6 and 8 
Summary of changes in electrocardiogram (ECG) and physical examination (including BW) from baseline to Week 4 (for ECG only) and Week 8

Procedures:	
All subjects will be screened (following written informed consent) to assess eligibility for the study.
 
At the screening visit, all subjects will have a physical examination and an ECG performed and blood parameters assessed. If the subject is eligible, they will be randomised at the Baseline visit to receive FCM or IS (with dose as described in the Treatment Section). Study subjects may be hospitalised for study drug application, if needed, at the discretion of the Investigator.
 
Subjects randomised to receive FCM will receive a second and third administration on Day 8 and Day 15, if needed. For subjects randomised to receive Venofer additional dosing visits are required three times a week up to Week 4 to achieve total iron repletion.
 
All subjects will be required to attend follow-up visits at Weeks 2, 4, 6 and an end of study visit at Week 8 (or earlier if discontinued prematurely). At each visit, all subjects will have their vital signs and blood parameters assessed (using central laboratory). An ECG will be performed at Week 4 and Week 8.

	
Data will be recorded in the case report form (CRF) after each visit.
 
See Schedule of Events for full details of protocol required procedures and applicable visits (and timings).

Sample Size:	
A total of 368 subjects will be randomised (i.e. 184 per treatment group)
 
The sample size is based on showing non-inferiority in the difference in the proportion of subjects achieving an increase in Hb of $\geq 2\text{g/dL}$ at any time up to Week 8 between FCM and IS. Applying a test at a one sided alpha level of 2.5%, and a -15% non-inferiority margin, 147 subjects per-group will have a 80% power to detect whether FCM is non-inferior to IS with an expected IS responder proportion of 70%. The total sample size is 368, which allows for an estimated drop-out rate of 20% of the randomised subjects.

Statistical Methods:	
Primary endpoint:
 
Non-inferiority of FCM versus IS will be assessed by the difference in the proportion of subjects achieving an increase in Hb of $\geq 2\text{g/dL}$ at any time up to Week 8. The analysis will be performed for the Per Protocol set (PPS) and tested at a one sided alpha level of 2.5% with a 15% non-inferiority margin. A sensitivity analysis will be performed on the Full Analysis Set (FAS).
 
Secondary endpoints for efficacy:
 
All secondary endpoints will be analysed on the FAS and the PPS. All statistical tests will be performed at a 5% level.
 
Safety analysis
 
All safety analyses will be performed on the Safety Set. Further details will be specified in the Statistical Analysis Plan (SAP).

SCHEMA

↓ = Ferric carboxymaltose administration. Second and third administration only if needed according to dosing table

↑ = Iron Sucrose administration. Subjects will be required to visit the study centre for administration of 200 mg IS three times a week until individually calculated iron dose is achieved.

Table 1: Schedule of Events

Procedures	Visit			
	Visit 1 Screen	Visit 2 Baseline	Visit 3-5	Visit 6 End of study/ Early Termination
	Day -7 to Day -1	Day 1	Weeks 2, 4, 6 ±3 Days	Week 8 ±4 Days
Informed consent	✓			
Eligibility criteria	✓	✓ ⁽¹⁾		
Demographics	✓			
Medical history	✓			
Physical examination and weight	✓			✓
Height	✓			
Vital signs (blood pressure, heart rate, temperature)	✓	✓	✓	✓
Electrocardiogram	✓		✓ ⁽⁶⁾	✓
Laboratory assessments (haematology/ biochemistry/iron parameters) ⁽²⁾	✓	✓	✓	✓
Hepatitis B and C screening ⁽³⁾	✓			
Urinalysis ⁽⁴⁾	✓		✓	✓
Serum pregnancy test ⁽⁵⁾	✓			✓
Adverse events	✓	✓	✓	✓
Prior & Concomitant medications	✓	✓	✓	✓
Randomisation		✓		
Administration of study drug		✓	(✓ ⁽⁷⁾)	

1. Laboratory parameters will be tested at Baseline but will not be used for eligibility because the results will not be available on time. Laboratory parameters taken at screening will be checked for eligibility at Baseline

2. Laboratory assessments include:

- Haematology: Hb, haematocrit, red blood cell count, MCV, MCH, MCHC, reticulocyte count, Hb content in reticulocytes, white blood cell count with differential and platelet count.
- Iron status parameters: serum iron, serum ferritin, serum transferrin, UIBC and TSAT.
- Biochemistry parameters: electrolyte status (sodium, potassium, magnesium, calcium, chloride, phosphorus), AST, ALT, gamma-glutamyl transpeptidase (GGT), glucose, alkaline phosphatase (AP), lactate dehydrogenase (LDH), hsCRP.

3. Hepatitis screening consists of Hepatitis B antigen, Hepatitis B virus DNA and Hepatitis C virus antibody

4. Urinalysis includes: phosphorus, protein, glucose, bilirubin, pH, nitrite, ketone, urobilinogen, blood, leukocytes

5. For women of childbearing potential only.

6. ECG is only performed at Week 4.

7. Subjects randomised to receive FCM will receive a maximum of 1,000 mg at Baseline (Day 1), a second administration of a maximum of 1,000 mg at Day 8 and a third administration of a maximum of 500 mg at Day 15, if applicable. Subjects randomised to Venofer will need to come to the study centre to receive further Venofer dosing three times a week. All study procedures must be conducted prior to dosing.

Notes: ALT = alanine aminotransferase; AP = alkaline phosphatase; AST = aspartate aminotransferase; hsCRP = high sensitive C-reactive protein; ECG = Electrocardiogram; FCM = ferric carboxymaltose; GGT = gamma glutamyl transpeptidase, Hb = Haemoglobin; LDH =lactate dehydrogenase,MCH = Mean corpuscular Hb; MCHC = Mean corpuscular haemoglobin concentration; MCV = Mean corpuscular volume; TSAT = Transferrin saturation, UIBC= unsaturated iron binding capacity.

TABLE OF CONTENTS

	Page
SIGNATURE PAGE.....	2
INVESTIGATOR AGREEMENT AND SIGNATURE PAGE.....	3
SYNOPSIS	4
SCHEMA.....	10
TABLE OF CONTENTS	13
LIST OF ABBREVIATIONS	18
1. INTRODUCTION AND BACKGROUND.....	20
1.1 Background of the Disease and Treatment Options	20
1.2 Summary of Ferric Carboxymaltose Nonclinical and Clinical Data	21
1.2.1 Pharmacology	21
1.2.2 Preclinical and Pharmacokinetic Studies.....	21
1.2.3 Efficacy.....	22
1.2.4 Safety	23
2. RATIONALE	25
2.1 Design	26
2.2 Dose and Drug Selection	26
2.3 Endpoint and Procedures	27
2.3.1 Primary Endpoint.....	27
2.3.2 Secondary Endpoints	28
2.4 Key Inclusion and Exclusion Criteria.....	28
3. STUDY OBJECTIVES.....	29
3.1 Primary Objective	29
3.2 Secondary Objectives.....	29
4. INVESTIGATIONAL PLAN	30
4.1 Overall Study Design.....	30
4.2 Duration of Subject Participation and Study	30
5. SELECTION AND WITHDRAWAL OF SUBJECTS	31
5.1 Number of Subjects.....	31
5.2 Inclusion Criteria	31
5.3 Exclusion Criteria	31
5.4 Withdrawal of Subjects.....	33
5.4.1 Withdrawal of Subjects from Study Drug	33

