5.4.2 Withdrawal of Subjects from Study Visits

Subjects may voluntarily withdraw from study participation at any time without having to provide a reason. Subjects may be withdrawn because of the appearance of a new health condition which may require care or medications prohibited by the protocol, unacceptable AEs, refusal to continue treatment, or at the Investigator's discretion if it is in the subject's best interest.

If a subject withdraws from the study at any time either at his or her request or at the Investigator's discretion, the reason(s), including the primary reason for withdrawal, if provided by the subject, should be recorded. Subjects who discontinue the study prematurely should undergo all End of Study assessments, if possible.

Subjects may be withdrawn by the Investigator and their study participation discontinued prematurely for several reasons. Discontinuation from the study is **mandatory** in the following circumstances:

- The subject requires blood transfusion or ESA treatment (e.g. for excessive acute bleeding) or intake of iron preparations other than the study drug. If possible, discontinuation assessments should take place before transfusion or treatment. The reason for discontinuation and the date must be recorded on the appropriate page of the case report form (CRF). The date on which the procedure actually took place should also be recorded on the CRF.
- Surgery with expected significant blood loss.
- Development of an illness, condition, or procedural complication, which would interfere with the subject's continued participation.
- The Investigator/study physician feels it is medically in the best interest of the subject to discontinue the subject's participation in the study.
- Pregnancy (to be recorded on the specific pregnancy reporting form).

Subjects may be discontinued from the study for the following reasons (reason to be recorded on the appropriate page of the CRF):

- Subject does not comply with study procedures.

Appropriate documentation will be kept for all subjects who are enrolled into the study (i.e., who provide written informed consent). All subjects who discontinue from the study will be strongly encouraged to have all assessments for the End of Study visit (Visit 6) performed.

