6. RANDOMISATION, BLINDING AND UNBLINDING PROCEDURES

6.1 Randomisation

An Interactive Response Technology (IRT) system will be used in the study. A separate user manual that outlines the details of IRT will be provided to the sites.

All subjects screened must be identifiable throughout the study and will be given a unique study subject number. Each site will be identified by a 3 digit number, and subject numbering will be assigned by IRT. The Investigator will maintain a list of subject numbers and subject names to enable records to be matched at a later date.

Randomisation of eligible subjects will be performed before start of treatment with study drug. Randomisation will be performed based on a pre-defined, computer generated randomisation list. The subjects will be randomised 1:1 to receive either FCM administration(s) or IS. IRT will be contacted for treatment assignment following confirmation of eligibility at the Baseline visit.

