11.2 Sample Size and Power Calculations

To assess the non-inferiority of FCM compared to IS in the proportion of subjects who will have an increase from baseline in Hb of $\geq 2\text{g/dL}$ at any time up to Week 8 (responders), the following assumptions have been made:

- Subjects that will be included in the study will be mainly subjects with GI disorders and women with HUB. The responder rate after IS treatment is expected to be 70%. This is based on the mean of the proportion of responders in the 2 studies described below in IDA subjects with IBD and IDA subjects with HUB respectively.

In study FER-IBD-07-COR, which compared FCM to IS in IDA subjects with IBD, the proportion of subjects who had an increase from baseline in Hb $\geq 2\text{g/dL}$ at Week 8 was 72% in FCM group and 55% in IS group (Per Protocol Set (PPS)). Seventy three percent in the FCM group and 58% in the IS group had an increase of at least $\geq 2\text{g/dL}$ at any time up to Week 8.

In study 1VIT04002/1VIT04003, which compared FCM to oral iron in IDA subjects with HUB, 82% of subjects in the FCM group had an increase from baseline in Hb $\geq 2\text{g/dL}$ at any time up to Week 6. Although no subjects in this study were treated with Venofer, and no other data are available from studies in which HUB patients are treated with Venofer, it has been assumed that Venofer would have the same response rate as FCM in this patient population.

- The non-inferiority margin for the difference in the proportion of responders between FCM and IS was set to -15%. This margin will ensure a treatment effect for FCM ($70 - 15 = 55$) greater than 33%, the upper bound of the 95% confidence interval (CI) of the proportion of responder of an estimated placebo effect, by more than half the effect itself ($33 + 16.5 = 49.5$). The placebo effect was estimated as follows:

In study 1VIT07017 which compared FCM to Standard Medical Care (SMC) in IDA subjects with HUB or post-partum, there were 55 subjects in the SMC group who did not receive any Iron treatment. Of these, 50 had a Hb assessment at Day

30. At Day 30 the proportion of non-treated subjects with an Hb increase ≥ 2 g/dL was 22% (11/50) with a 95% CI from 11% to 33%.

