The sample size is based on showing non-inferiority in the difference in the proportion of subjects achieving an increase in Hb of ≥ 2 g/dL at any time up to Week 8 between FCM and IS. Applying a test at a one-sided alpha level of 2.5%, and a -15% non-inferiority margin, 147 subjects per group will have 80% power to detect that FCM is non-inferior to IS with an expected IS responder proportion of 70%. The total sample size is 368 (184 per treatment group), taking into account an estimated drop-out rate of 20% of the randomised subjects.

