3.3 Per Protocol Set

The Per-Protocol Set (PPS) is defined as all subjects in the FAS with a study drug compliance between 80 and 120% and do not have any major protocol violations ([appendix 1](#)).

The subjects in the PPS will be analysed based on the treatment that they were randomised to.

As per protocol, blood samples had to be drawn before study drug administration (when planned). All laboratory efficacy assessments (Hb, Ferritin, and TSAT) that are measured from a blood sample

taken after the study drug administration will not be considered for any efficacy analysis for both PPS and FAS. The subjects will still be in the PPS if they do not have a major protocol deviation.

For subjects who took prohibited concomitant medication, all laboratory efficacy assessments (Hb, Ferritin, and TSAT) will be censored after the prohibited medication start date for both PPS and FAS. The subjects will still be in the PPS if they do not have a major protocol deviation.

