	PROCEDURE OUTSIDE WINDOW # 3	ECG Out Of planned Window (Not done at Screening & Week 4 & EOS)	Minor
NON- COMPLIANCE WITH PROCEDURE	NON-COMPLIANCE WITH PROCEDURE #1	Dosing NOT performed after all study assessments for the visit(Out of chronological order is minor)	Minor
	NON-COMPLIANCE WITH PROCEDURE #2	Missing reporting of SAEs to sponsor within the agreed timeframe "within 24 hours of awareness"	Major
VISIT OUTSIDE WINDOW	VISIT OUTSIDE WINDOW # 1	Screening duration > 7 days	Minor
	VISIT OUTSIDE WINDOW # 2	visits out of window (Planned chronological visits schedule not respected is major)	Major
VIST NOT DONE	VISIT NOT DONE	Visits NOT done	Major

Vifor DVSCAT (Categories of PDs)	Vifor DVDECOD (Sub-Categories of PDs)	Details	Major or Minor
SUBJECT NOT WITHDRAWN AS PER PROTOCOL	SUBJECT NOT WITHDRAWN AS PER PROTOCOL	Site staff failed to take the appropriate action in response to protocol-specific discontinuation/withdraw criteria such as: severe anaemia (Hb <6 g/dL) and the subject continued the study	Major
OTHER	NON-COMPLIANCE WITH PROCEDURE # 1	Rescreening within 4 weeks of original screening visit(minor)	Minor
	NON-COMPLIANCE WITH PROCEDURE # 2	Race is not Chinese and subject randomized (minor)	Minor
	OTHER	Any other protocol deviation (e.g., as outlined in the monitoring plan):	TBD*
NOTE		*TBD (to be discussed): PDs will be determined of major or minor by TMM and consult with Sponsor if necessary CRA will submit the signed and dated major protocol deviation to local EC within 15 working days.	

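### SAP 3.3 drops Hb drawn after that day's dose from both PPS and FAS with no Hb-specific reason; the loss falls mostly on iron sucrose, but its expected effect is small

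*Protocol*

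**What the plan says.** Pre-dose sampling is mandatory in both arms (Protocol Table 1 footnote 7, 9.1.3 and 9.2.2). The footnote reads: "Venofer dosing three times a week. All study procedures must be conducted prior to dosing".

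SAP 3.3 covers the case where a site does not comply. Hb, ferritin and TSAT from a sample "taken after the study drug administration will not be considered for any efficacy analysis for both PPS and FAS". The subject stays in the PPS unless there is a separate major deviation. Appendix 1 grades the order error as minor: "Dosing NOT performed after all study assessments for the visit(Out of chronological order is minor".

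Missing data are not imputed (SAP 4.1.8). The only sensitivity analysis of the primary endpoint is the FAS (SAP 4.1.6), and SAP 4.9 plans no other analyses.

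On timing, IS is given three times a week up to Week 4, with at most 11 injections (Protocol synopsis and 7.2.2). FCM is given on Day 1 and, where needed, Day 8. Only subjects of 35 to under 50 kg with Hb below 10 g/dL also have a Day 15 dose (Protocol 7.2.1). Blood is scheduled at baseline and Weeks 2, 4, 6 and 8. For early leavers, "Subjects who discontinue the study prematurely should undergo all End of Study assessments, if possible".

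**The concern.** The rule treats three analytes alike, although IV iron acts on them differently. Ferritin and TSAT can change directly with iron just infused, so excluding them is sensible. For post-baseline Hb the documents offer no such reason. Protocol 1.2.3 describes the Hb increase as emerging within about four weeks. Iron given minutes earlier is not yet haemoglobin, and the infused volume can only lower the reading.

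The opportunity for loss is also unequal. After baseline, a dose and a scheduled blood draw fall on the same day mostly in the IS arm. The primary endpoint counts a response at any time up to Week 8. A discarded Hb can therefore remove an IS response but never add one, which makes non-inferiority easier to show. Because PPS and FAS share the rule, agreement between them gives no reassurance on this point.

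**Working it through.** **1. The plan's own figure.** Inputs from Protocol 11.2: "Applying a test at a one-sided alpha level of 2.5%, and a -15% non-inferiority margin, 147 subjects per group will have 80% power", and "The responder rate after IS treatment is expected to be 70"%, which is the mean of 58% and 82%. Allocation is 1:1 (Protocol 6.1), and the FCM rate is taken as equal.

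n = (1.960 + 0.842)² × 2 × 0.70 × 0.30 / 0.15² ≈ 146.5, so 147 per group. With 20% drop-out, 147 / 0.80 = 183.75, so 184 per group and 368 in total. Both figures reproduce.

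**2. Which visits are exposed.** Three doses a week on an assumed Monday/Wednesday/Friday calendar, Monday start, give Days 1, 3, 5, 8, 10, 12, 15, 17, 19, 22 and 24.
- Protocol 2.1's example (65 kg, Hb 9 g/dL): 65 × (15 − 9) × 2.4 + 500 = 1,436 mg, or 7 doses. Days 12 and 15 fall inside the Week 2 window (Days 11-17).
- A 40 kg subject with Hb 9 g/dL: 40 × 6 × 2.4 + 500 = 1,076 mg, or 5 doses. The course ends on Day 10, before that window.
- The 11th dose falls on Day 24 (Monday or Wednesday start) or Day 25 (Friday start). The Week 4 window (Days 25-31) is touched only at its edge, or after delays.
- The SAP 4.5 compliance table runs to 2,400 mg, which is 12 doses, against the protocol's 11. A 12th dose would fall on Day 26 or 27, inside the Week 4 window. The two passages should be reconciled.
- No dosing is planned at Weeks 6 or 8.
- FCM: Day 8 has no scheduled draw. Day 15 matters only for the low-weight, low-Hb subgroup, whose share is not given.

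For completers the rule therefore reaches essentially the Week 2 value. An IS responder is lost only if the rise was seen at Week 2 and not at Weeks 4, 6 or 8.

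**3. Size among completers.** In the IBD study cited in Protocol 11.2, IS response was 58% at any time and 55% at Week 8. The difference of 3 points is what would be lost if every value before Week 8 disappeared in every IS subject. The documents give no rate of out-of-order sampling. Assuming 5-20% of IS subjects are affected, the loss is 0.05 × 3 = 0.15 to 0.20 × 3 = 0.6 points. This leans high, because the 3 points cover all visits before Week 8 and not Week 2 alone.

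**4. Effect on the test.** Exact binomial enumeration, 147 per arm, using the SAP 4.6.1 interval (Newcombe with continuity correction). Success means a lower bound above −15%. Type I error is taken at true rates of FCM 55% and IS 70%, and power at 70% in both arms.

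| Loss in observed IS rate (points) | Type I error | Power |
|---|---|---|
| 0 | 2.2% | 78.7% |
| 0.3 | 2.5% | 80.2% |
| 0.6 | 2.9% | 81.6% |
| 1 | 3.4% | 83.4% |
| 2 | 5.0% | 87.3% |

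At 0.15 points the type I error is about 2.4%. The rows for 1 and 2 points show sensitivity only; nothing in the documents supports losses of that size.

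**The case against.** The strongest reply is that the schedule creates an opportunity and not a loss. Pre-dose sampling is compulsory, a value disappears only after a site error, and no error rate is given. The footnote quoted above is the safeguard, not the defect. This stands, and it is why the effect is small. A single pre-specified rule for all three analytes is also tidy, but tidiness is not a reason to discard valid Hb.

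The reply that the values will be visible anyway stands only in part. Unused data are to be flagged in listings (Protocol 11.7.2) and all laboratory results are listed (SAP 4.7.2). No planned table or analysis shows their effect by arm.

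A reader might infer three stronger things that the documents do not support:
- **That losses occur almost only under IS.** Mostly is accurate. Day 15 exposes some FCM subjects. On Day 1 both arms are dosed, and a discarded baseline would fall back to screening.
- **That early leavers add a large further bias.** The share with a post-dose last sample and their response rate are both unknown. The 147 is already net of the 20% drop-out. Missed visits and missing haematology assessments are major deviations in Appendix 1, so the PPS status of these subjects is unclear. After a reaction a subject may stay in the study and keep attending visits (Protocol 5.4.1).
- **That losing subjects from both sets also favours FCM.** SAP 3.3 removes values and does not say that it changes set membership. If subjects did leave, the direction could reverse. Suppose 2-6% of the IS arm left, with 20-40% response. The IS rate would rise by 0.02 × (0.70 − 0.40) / 0.98 = 0.6 points to 0.06 × (0.70 − 0.20) / 0.94 = 3.2 points, which works against FCM.

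**Conclusion.** The point holds as a small, avoidable, directional weakness. SAP 3.3 discards post-baseline Hb without an Hb-specific reason, mostly in the comparator arm. Among subjects who stay in the analysis, the loss can only lower the any-time IS response, and neither planned analysis would reveal it.

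On the assumed 0.15 to 0.6 points, type I error at the margin goes from 2.2% to 2.4-2.9%, which is close to the nominal 2.5%. This rests on the assumed 5-20% deviation rate, an assumed dosing calendar, and one IBD study whose analysis set for the 58% is not clearly stated. The 3 points are therefore a guide and not a strict bound.

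The Week 2 secondary endpoints are affected more directly, because no later visit can replace a discarded Week 2 value.

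The SAP sentence does not say that it means the same day's dose. Read literally, it would exclude every post-baseline sample. The preceding sentence, about drawing blood before a planned administration, shows that this is not intended, but the wording should say so.

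**What to change.** In SAP 3.3, before database lock:
- State that the rule concerns samples drawn after that same day's dose.
- Limit the exclusion to ferritin and TSAT, and to a post-dose Day 1 Hb that would serve as baseline, where dilution could create a false rise.
- Keep all other post-baseline Hb, including early-termination Hb, whatever its order relative to that day's dose. The separate censoring after prohibited medication is unaffected.
- Report out-of-order Hb values by arm and visit, and give the primary result with and without them.

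The cost is about two lines of SAP text, one small table and one extra run. The sample size stays at 147 evaluable per group and 368 in total. The downside is that a few retained Hb values may be slightly low from the infused volume, which can only work against calling a response.
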